The doses to be tested for famotidine are 20 mg thrice daily, 40 mg thrice daily, 80 mg thrice daily and no famotidine. The doses to be tested for n-acetyl cysteine are 600 mg thrice daily, 1200 mg thrice daily and 1800 mg thrice daily. The dose combinations are labelled 1 through 12 and are zoned as illustrated in Figure 10. The first zone has the combination of the lowest dose of each drug. The second zone has the combination of the lowest dose of each drug with the middle dose of each drug. The dose escalation starts with the first zone and follows with the second zone and then each combination of doses in the zone next closest to the coordinate

[figure not shown]

Figure 10. Dose Combinations of N-Acetyl Cysteine and Famotidine

origin shown in figure 10. Combination doses in the same zone are tested simultaneously using block randomization to control the number of patients for each open dose. Some combinations doses may close, in which case blocked randomization is applied to the remaining open combination doses in the same zone. A modified “3+3” design¹⁷² will be used for the initial dose escalation.

To find acceptable dose levels any grade 3 or higher toxicity will be considered a dose-limiting toxicity (DLT). The modified “3+3” design proceeds as described below. Three patients receive dose level 1. Their responses determine the subsequent steps as described in the following decision rules.

- (1) If two patients (2/3) experience DLT, then we close dose level 1 and all larger doses to testing.
- (2) If no patient experiences DLT, then we designate dose level 1 as an admissible dose, and open doses in zone 2 for testing.
- (3) If only one of the first three patients (1/3) experiences DLT, then we assign three more patients to dose level 1. In this case, we assign up to six patients to this dose, and the following decision rules apply:
 - a. If only one of the six patients (1/6) experiences DLT, then we designate dose level 1 as an admissible dose, and open doses in zone 2 for testing.
 - b. If two of the six patients (2/6) experience DLT, then we designate dose level 1 as an admissible dose, and doses in zone 2 and higher are closed to testing.
 - c. If more than two of the six patients (>2/6) experience DLT, then we close dose level 1 to testing, and we also close doses in zone 2 and higher.

ii) Study Procedure

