Subjects will be expected to take the dose combination to which they are as assigned and as prescribed. Subjects will record dates and times each medication dose was taken on their log forms which will be collected weekly. Subjects will be contact at least weekly by a Research Assistant to monitor symptoms, verify compliance with study drugs and compliance with completing medication logs and daily diary. The Research Assistant will also administer a CAP-SYM 18 during this call. The Research Assistant will communicate any concerns and all findings to a study Investigator who will later call the subject to assess how the subject is doing, discuss any concerns and will monitor the subject in the performance of a 40 Step Test for those subjects provided with an electronic device capable of measuring an Oxygen Saturation level unless the Investigator is concerned about the safety of doing so. Subjects will collect a urine sample weekly. The urine samples and the daily diary and medication log CRFs completed by the subject will be delivered by the subject or a family member within 4 hours of collection by means of the COVID-19 testing car line at Greenville Memorial Hospital. The urine specimens will be sent to Kiyatec® to measure the subject's F2-Isoprostane level, creatinine level, a cytokine panel (IL-1β, IL-2, IL-6, IL-8, IL-10, IFNγ, TNFα and GM-CSF), n-methylhistamine level and TMRSS2 levels. Subjects will self-isolate per current CDC recommendations. Subjects will remain on medication for a minimum of 7 days and unless hospitalized will continue on the medications until it has been more than 10 days beyond the start of symptoms, symptoms have improved and the subject has been without a fever for at least 24 hours without the use of a fever reducing medication. If subjects are hospitalized, then the will instructed to discontinue taking the study medications. After discontinuing study drugs for any reason, the subject will have their blood will be drawn to measure Glutathione level, a cytokine panel (IL-1β, IL-2, IL-6, IL-8, IL-10, IFNγ, TNFα and GM-CSF), and

their tryptase level; and a urine sample will be collected to measure the subject's F2-Isoprostane level, creatinine level, a cytokine panel (IL-1 β , IL-2, IL-6, IL-8, IL-10, IFN γ , TNF α and GM-CSF), n-methylhistamine level and TMRSS2 levels.

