Subjects will be contacted weekly at minimum by the assigned Research Assistant and the assigned Investigator. It will be the responsibility of the assigned Investigator to ensure this happens correctly. Depending how a subject is doing clinically, an Investigator will have the discretion to perform more frequent contacts. These contacts will preferably be done with both a video and audio connection for which the Vivify® devices are capable. A telephonic contact will be discouraged but will be permissible for those who do not have a Vivify® device or for whom an acceptable audio-video connection cannot otherwise be established. Data will be collected and recorded for these contacts on the appropriate REDCap® form, i.e., Research Assistant Weekly Assessment, or Investigator Weekly Assessment. It will be the responsibility of the assigned Research Assistant to enter weekly data from the patient's medication log and daily diaries into the REDCap® forms, Daily Medication Log and Daily Diary. If any new medications are started or any non-trial medications are changed by either the Investigator or any other provider involved in the subject's care as documented in EPIC, the Research Investigator will document such changes using the REDCap® form, New Medications. At the end of every evaluation by the assigned Investigator, the Investigator will document in the REDCap® form their assessment which must be one of the following: 1, Continue on Study Without Change; 2, Have made arrangements for short interval follow-up with myself; 3, Discontinue Study; 4, Recommend Evaluation in ER; 5, Recommend Evaluation by Primary Provider; 6, Recommend Dose Reduction in one or both Trial Medications. If the Investigator Documents any assessment other than "Continue on Study Without Change", an electronic notification will immediately be sent to the PI notifying the PI of the Investigator's Assessment. If the Investigator's assessment is to recommend a dose reduction, they will be directed to document such on the REDCap® form, Trial Drug Adjustment. Within this form, the new dosages will be documented, to include the possibility of discontinuing either or both medications. Additionally, the Investigator will be required to identify whether the adjustment is being made due to a drug toxicity. If the Investigator documents that the adjustment is made due to a drug toxicity upon saving the form an immediate electronic notification will be made to the PI and Chair of the DSMB. The PI will then complete the REDCap form "NCI Adverse Event Serious Adverse Event CTCAE v5." This is an extensive form for which the PI will complete for any AE or SAE. It is comprehensive as it includes the entirety of the CTCAE v5 to include every possible grade of toxicity. Through branching logic, it minimizes the task of data entry only to the particular organ systems or laboratory values involved, an allows the PI to easily document all the data necessary for AE and SAE determination so that the IRB, DSMB and FDA can all be notified as necessary and within the required timelines as described more fully in the "Protection Against Risk" section below.

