Data will be exported from REDCap[®] using the Data Export Tool into a format that can be analyzed using R, JMP and/or SAS (SAS, Cary, NC). The User Rights in REDCap[®] will restrict the use of the REDCap[®] "Data Export Tool" to only the PI, Epidemiologist and the Statistical Co-Investigators. The rights will be further restricted within REDCap[®] such that only De-Identified data can be exported from Data Export Tool. Therefore, because no date or time fields can be extracted from REDCap[®] as described above, any Data Entry Form within REDCap[®] that collects a date has been created to include a hidden calculation field to calculate and store the number of days between such a date and either the enrollment date or the medication start date. Some dates are calculated based on the medication start date to make data collection easier on certain forms; however, the number of days between enrollment and medication start is also calculated and stored so that any number of elapsed days can easily be determined from either. After the data has been exported from REDCap into an aforementioned statistical package and descriptive statistics have been generated and analyzed by the Statistical Investigators. These results will be shared with the Epidemiologist and all Investigators so that appropriate conclusions can be reached and ultimately disseminated.

vi) Limitations of the Proposed Study Design

This is a phase I trial and may be limited by unmeasured confounders such as clinical practice patterns of the providers ordering initial SARS-CoV-2 testing. It also may be limited as subjects are being recruited directly from the ED and thus may be more symptomatic or have other unmeasured cofounders as compared to the general population who may become infected with SARS-CoV-2.

IV) PROTECTION OF HUMAN SUBJECTS

i) Risks To The Subjects

The main risks to Famotidine which have been occurred in greater than or equal to 1% of subjects in clinical trials are headache; dizziness and constipation.

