Assessment	Enrollment (within 24 hours of a SARS CoV-2 Test)	Weekly after Randomization Until Hospital Admission or Study Completion	Upon Study Completion (If SARS CoV-2 Positive)	If Hospitalized and Until Discharge
Informed Consent	X			
Urine Pregnancy Test (If appropriate)	X			
Blood Type and Rh	X			
(Serum) Cytokines (IL-1 β , IL-2, IL-6, IL-8, IL-10, IFN γ , TNF α and GM-CSF), Tryptase and Glutathione Level	X		X	X (once upon hospitalization)
(Urine) F2-Isoprostane/Creatinine Ratio, TMRSS2 Cytokines (IL-1 β , IL-2, IL-6, IL-8, IL-10, IFN γ , TNF α and GM-CSF) and N-methylhistamine	X	X	X	X (once upon hospitalization)
CURB-65 Score	X			
CAP-Sym 18	X			
IPSS (men only)	X			
Weekly Review of Daily Medication Logs and Daily Diary		X		
Weekly Assessment CRFs		X		
Completion Data CRF				
Hospital Tracking CRFs				
			X	X

Medication Log Form

Medication Log Form: Trial of FAM and NAC for SARS-CoV-2							
Subject Study Number: _____				Week #: _____			
Day of Week Trial Started: _____ (fill this in by hand under Day 1 below)							
Dose of Famotidine 20 mg tablets Assigned to Taken Thrice Daily: 0 1 2 3 (Research Staff to Circle)							
Number of N-Acetyl Cysteine Capsules Assigned to Take Thrice Daily: 1 2 3 (Research Staff to Circle)							
	Day 1	Day 2	Day 3	Day 4	Day 5	Day 6	Day 7
Day of Week							
Date (MM/DD)							
Famotidine (20 mg tablet)							
1 st Dose							
2 nd Dose							
3 rd Dose							
N-Acetyl Cysteine (600 mg capsule)							
1 st Dose							
2 nd Dose							
3 rd Dose							

Instructions for Research Staff:

1. Print a minimum of 4 Sheets and enter Subject Study Number on each. Write in week numbers 1 to 4 on each sheet.
2. Enter Day of Week Subject is to start taking medicine. This should be the same for each sheet.
3. Under Day 1 enter the day of the week that subject is to start taking medicine. Under each subsequent Day enter the next day of the week.
4. Circle the assigned number of Famotidine tablets to take thrice daily.
5. Circle the assigned number of N-Acetyl Cysteine capsules to take thrice daily.

Instructions for Research Subject:

1. You will be assigned to take one, two or three Famotidine tablets three times a day. Please enter the time of day for the correct day for each dose you take.
2. You will take the N-Acetyl Cysteine capsules thrice a day. You will be assigned to take one, two or three capsules each time. Please enter the time of day for the correct day for each dose you take.

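### The paper medication log has no field for the number of tablets or capsules taken, so a part-taken dose is logged like a full one

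*Combined protocol and SAP*

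**What the plan says.** **The form (IX Appendices, Medication Log Form).** Each drug has one cell per dose, three per day, seven days per sheet. For both drugs the subject's instruction is "Please enter the time of day for the correct day for each dose you take". Staff mark the unit count beforehand: "Circle the assigned number of N-Acetyl Cysteine capsules to take thrice daily". The subject is told of NAC: "You will be assigned to take one, two or three capsules each time". The famotidine line offers 0, 1, 2 or 3 tablets of 20 mg.

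**The protocol body (III, ii, Study Procedure).** It describes the same content: "Subjects will record dates and times each medication dose was taken on their log forms which will be collected weekly". A Research Assistant contacts each subject at least weekly and checks, among other things, that the study drugs are being taken. An Investigator calls afterwards.

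**Dose levels (III, i, Study Design).** NAC is given at "600 mg thrice daily, 1200 mg thrice daily and 1800 mg thrice daily". For famotidine: "The doses to be tested for famotidine are 20 mg thrice daily, 40 mg thrice daily, 80 mg thrice daily and no famotidine".

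**Dose changes (III, iv, e, Outpatient Follow-up).** Reductions recommended by the Investigator go on the Trial Drug Adjustment form: "Within this form, the new dosages will be documented, to include the possibility of discontinuing either or both medications". The same section has the Research Assistant enter the paper log into a REDCap form called Daily Medication Log.

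**Escalation (III, i).** A toxicity of grade 3 or above is a DLT. No DLT in three subjects, or one in six, makes the level admissible and opens the next zone. The rule attaches no condition about how much drug was taken.

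**The concern.** NAC capsules are all 600 mg, so the three NAC levels differ only in how many capsules are swallowed at each intake. That number is what a dose-finding trial most needs to know about exposure, and the paper log does not ask for it.

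Self-reduction is foreseeable. The protocol's own section on NAC side effects cites a phase I trial of 600, 1200 and 1800 mg in which 9 of 11 drug-related events were gastrointestinal and 3 of the 11 resolved on reduction from three to two doses a day. A subject with nausea may simply take fewer capsules. If that happens mainly where tolerability is worst, the absence of DLTs in a high arm partly reflects a lower dose than the one being declared admissible. Safety of the combination is Aim 1, and arms start with three subjects.

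**Working it through.** There is no planned figure to reproduce, because the point concerns data capture. The check has four parts.

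**1. What the log cannot tell apart.** Inputs: 600 mg capsules, three intakes a day, 1 to 3 capsules per intake. Daily NAC = capsules taken × 600 × 3.

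| Assigned per intake | Taken per intake | Implied by log (mg/day) | Actual (mg/day) |
|---|---|---|---|
| 3 | 3 | 5400 | 5400 |
| 3 | 2 | 5400 | 3600 |
| 3 | 1 | 5400 | 1800 |
| 2 | 2 | 3600 | 3600 |
| 2 | 1 | 3600 | 1800 |
| 1 | 1 | 1800 | 1800 |

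One of three capsules at every intake gives the daily total of the lowest NAC level, logged as the highest. A dose missed altogether shows as an empty cell.

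**2. How many arms are exposed.** There are 4 famotidine × 3 NAC = 12 combinations. With whole units, a dose cannot be part-taken when NAC is one capsule and famotidine is none or one tablet: 1 × 2 = 2 combinations. The other 12 − 2 = 10 are exposed, assuming the 80 mg famotidine level is given as more than one tablet. If it were a single unit, 9 would be.

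**3. Size of the effect on escalation (illustrative).** The documents give no adherence figure and no DLT rate under partial dosing, so the rates here are assumptions. The rules are written for dose level 1, and I apply them to any single level. With true DLT rate p:

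P(level passes and next zone opens) = P(0/3) + P(1/3) × P(0/3) = (1−p)³ + 3p(1−p)⁵

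- p = 0.30: 0.343 + 0.151 = 0.49
- p = 0.20: 0.512 + 0.197 = 0.71
- p = 0.10: 0.729 + 0.177 = 0.91
- p = 0.08, the top of the protocol's own assumed DLT range: 0.779 + 0.158 = 0.94

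If partial dosing throughout an arm lowered a 30% rate to 10–20%, the chance of passing would rise from 0.49 to 0.71–0.91. If only one of the first three subjects part-dosed (10%) and everyone else had 30%:

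- P(0/3) = 0.9 × 0.7² = 0.441
- P(1/3) = 0.1 × 0.7² + 0.9 × 2 × 0.3 × 0.7 = 0.427
- P(pass) = 0.441 + 0.427 × 0.343 = 0.59

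So a single subject shifts 0.49 to 0.59. At the 5–8% rates the protocol assumes, a level nearly always passes and partial dosing changes little.

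**4. The famotidine line on the same form.** 80 ÷ 20 = 4 tablets. The form allows 0 to 3, which is 0, 20, 40 or 60 mg per intake. The 80 mg level cannot be circled, and 60 mg is not a listed level. The subject's instruction also speaks of one, two or three tablets and leaves out the no-famotidine arms.

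**The case against.** The log is not the only exposure source. The weekly check on whether the drugs are being taken is listed separately from the check on completing the log, findings go to an Investigator, and each contact has its own REDCap form. A subject who had cut capsules could well be identified there. A reader might infer that partial dosing would go undetected in this trial; the documents do not support that. What stands is that the method is not described. Without a written count, the contact relies on recall of up to 2 drugs × 3 intakes × 7 days = 42 intakes.

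The fields of the REDCap Daily Medication Log and of the weekly assessment forms are in an attachment that was not supplied, so it cannot be said that the database lacks a count. But the Daily Medication Log is filled from the paper sheet, and transcription cannot supply a number the subject was never asked to write.

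A reader might also infer that a dose cut by the Investigator is lost because the circled number stays put. It is not: the Trial Drug Adjustment form holds the new dose. Nor does the statement in Data Analysis Methods that "no date or time fields can be extracted from" REDCap bear on this point. Losing clock times on export is a different matter from whether counts were collected, and the unseen form may hold intake in another way.

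Finally, judging a self-administered regimen as assigned is a recognised approach, and escalating on assigned level is not in itself an error. That stands, and the fix leaves the rule alone.

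**Conclusion.** The point holds for the paper log. It has no field for units taken, so in about 10 of the 12 combinations a self-reduced dose is recorded as a full one, by as much as 5400 against 1800 mg/day of NAC. Only the weekly contact would reveal it, by a method the plan does not state. The supplied text describes no pill count and no minimum exposure for DLT evaluation.

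The documents do not show that any DLT would be credited to the wrong dose, or by how much escalation would be distorted. The shifts from 0.49 to 0.59, or to 0.71–0.91, rest on assumed DLT rates and assumed partial dosing. This is a cheap improvement to the exposure data behind the primary safety aim. It is worth making before enrolment because unrecorded counts cannot be reliably reconstructed later.

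The famotidine mismatch needs no assumption: the Study Design section and the log contradict each other on the 80 mg level.

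**What to change.** 1. Print a number-taken box beside the time in each dose cell, with 0 entered when none is taken.
2. Carry it as a numeric field in the REDCap Daily Medication Log, if one is not already there.
3. Add a descriptive table of AEs and DLTs by the dose actually being taken at onset, drawing on this field and the Trial Drug Adjustment form, next to the summary by assigned arm. Leave the escalation rule on assigned dose.
4. State in Study Procedure how the weekly contact checks the counts.
5. Before reprinting, reconcile the famotidine levels in Study Design with the tablet options and subject instruction on the form.

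Cost: one extra digit per dose for the subject, one reprinted form, possibly one database field per drug, a sentence in the protocol and one table. Sample size and decision rules are unchanged.

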- All COVID-19 outside of the ED or inpatient setting is done at either Greenville Memorial Hospital's drive-through tent or Patewood's Team Member Care Center in the Prisma Health Upstate Market.
- Both positive and negative test results are received by the Prisma Health NP pool who review the results. Nurses and NPs communicate results to the patients via phone call. In that phone call, patients are instructed as to next steps and self-care.

Proposed New Additional Process:

- On a daily basis, the WQ for outstanding results is updated with tests collected the prior day.
- This WQ will be reviewed by the Nurse pool, under the leadership of the Business Health NPs. They will review the listing to determine if the patients have a PCP yet or not.
- For patients with a PCP, an InBasket message will be sent to the PCP's Clinical Pool with the following message:
 - "Your patient has been tested for COVID-19 as he/she is currently experiencing the signs and symptoms of the illness. Please schedule a video visit with this patient for Day 2 (tomorrow) as well as day 5 and 8. At each of these visits, please monitor the patient for worsening symptomatology, answer his/her questions, and ensure that he or she is maintaining quarantine. If at any time the patient experiences worsening of symptoms and further evaluation face-to-face is indicated, the patient may either be seen at the practice with appropriate PPE or may be directed to an MD360 for urgent care, unless his/her symptoms are severe enough to merit attention in an ED."
 - If a COVID-19 Positive patient or PUI will be sent to MD360 following any of these virtual visits, please refer to the workflow below.

- For patients without a PCP, the Business Health NP or nurse pool will direct the patient to the Physician Finder "New Patient Specialist team" in addition to submitting a Referral to Primary Care.
 - The New Patient Specialist will schedule the patient with a PCP and send the following message:
 - "This patient is new to you. He/she has been tested for COVID-19 as he/she is currently experiencing the signs and symptoms of the illness. Please schedule a video visit with this patient for Day 2 (tomorrow) as well as day 5 and 8. At each of these visits, please monitor the patient for worsening symptomatology, answer his/her questions, and ensure that he or she is maintaining quarantine. If at any time the patient experiences worsening of symptoms and further evaluation face-to-face is indicated, the patient may either be seen at the practice with appropriate PPE or may be directed to an MD360 for urgent care, unless his/her symptoms are severe enough to merit attention in an ED."
 - If a COVID-19 Positive patient or PUI will be sent to MD360 following any of these virtual visits, please refer to the workflow below.

Patients in need of in-person care will either be seen at a practice site or be referred to an MD360 location:

- There is onsite x-ray and testing available.
- If the PCP is referring a patient to MD360 for further evaluation, the PCP must notify MD360 by phone prior to sending the patient.
- PCP will inform the MD360 provider of the patient's current status and assessment needs.
- Patient will be advised to call the MD360 front desk prior to entering the facility.
- MD360 team member will wear appropriate PPE and meet the patient at the door. Will escort the patient directly to an exam room for further care.

Tip Sheet for Telehealth Encounter with COVID-19 Positive Patients and PUIs

The following questions are a guideline for the ambulatory provider to discuss in a telehealth encounter with a COVID-19 positive patient or a PUI. These visits are to be conducted on Day 2, 5, and 8 after a positive test. The goal is to help guide whether a patient needs a higher level of care.

1. What was your temperature today and yesterday?
 - *If still febrile on day 8, do another follow-up on day 12*
2. Are you able to get to the bathroom without getting SOB?
 - *If no and different from patient baseline → send to ED*
3. Do you feel light headed or dizzy?
4. Have you been able to eat and drink some?
 - *If not able to eat and also dizzy, check CMP for AKI/transaminitis vs consider ED*
5. Are you having any kind of chest pain?
 - *If yes - take more detailed history to sort out if it's musculoskeletal with coughing.*
 - *If patient has cardiac history and chest pain, consider ED*
6. Are you having nausea, vomiting or diarrhea?
